#### **5.4 Subject Compliance Monitoring**

All study drug and radiation treatments will be administered at the study site and recorded on the case report form (CRF) and captured in TrialMaster. All dosing records for each patient will be kept by the site. Patients will be administered nivolumab or ipilimumab in a clinic or hospital setting under supervision of appropriate study personnel. Radiation therapy will be administered at the study site.

Subjects who are significantly non-compliant (e.g., not complying with protocol required visits, assessments, and dosing instructions) may be withdrawn from the study by the investigator and/or sponsor. The investigator and/or sponsor have the right to discontinue a subject from study treatment or withdraw a patient from the study at any time.

All drug compliance records must be kept current and must be made available for inspection by the sponsor and regulatory agency inspectors.

#### **5.5 Receiving, Storage, Dispensing and Return**

##### **5.5.1 Receipt of Drug Supplies**

Bristol-Myers Squibb (BMS) will package and distribute the study drug to sites. The study drug will be shipped in transport cool containers (2°C to 8°C) that are monitored with temperature control devices. The study drug will be shipped to the investigational pharmacy at each site.

Upon receipt of the study treatment supplies, an inventory must be performed and a drug receipt log filled out and signed by the person accepting the shipment. It is important that the designated study staff counts and verifies that the shipment contains all the items noted in the shipment inventory. Any damaged or unusable study drug in a given shipment will be documented in the study files. The investigator must notify study sponsor of any damaged or unusable study treatments that were supplied to the investigator's site.

##### **5.5.2 Storage**

See above Section 5.1 for study drug storage and handling instructions.

##### **5.5.3 Dispensing of Study Drug**

CONFIDENTIAL

This material is the property of the NYU School of Medicine. Do not disclose or use except as authorized in writing by the study sponsor

The NYU Investigational pharmacist or their designee pharmacist or other qualified individual will be identified at each site to prepare nivolumab and ipilimumab for administration. See Section 5.3 for nivolumab and ipilimumab administration instructions.

All drug accountability records must be kept current. The investigator must be able to account for all opened and unopened study drug. These records should contain the dates, quantity, and study medication dispensed to each patient, returned from each patient (if applicable), and disposed of at the site or returned to the sponsor or designee. All accountability records must be made available for inspection by the sponsor and regulatory agency inspectors; photocopies must be provided to the sponsor at the conclusion of the study.

#### 5.5.4 Return or Destruction of Study Drug

##### **Retention of Drug Product Vials:**

All opened vials (full, partially full, and empty) may be destroyed at the site by the appropriate site personnel (e.g., pharmacist, study nurse/coordinator) following local environmental requirements and institutional policies. All destruction must be fully documented at the time of destruction on the investigational product accountability log, or equivalent document at the time of destruction.

If opened vials are not destroyed immediately following drug preparation, opened vials must be stored in sealed, clear plastic bags until destruction.

**All unopened vials must be destroyed at the end of the treatment period unless BMS provides separate instructions for return.**

##### **Retention of supplies:**

Normal saline solution may be disposed of according to local site procedures. Other items used in the dose preparation and administration should be disposed of according to local site procedures.

At the completion of the study, there will be a final reconciliation of drug shipped, drug consumed, and drug remaining. This reconciliation will be logged on the drug reconciliation form, signed and dated. Any discrepancies noted will be investigated, resolved, and documented prior to return or destruction of unused study drug. All unused and/or partially used investigational product will be destroyed at the site per institutional policy. It is the Investigator's responsibility to arrange for disposal of all empty containers, provided that procedures for proper disposal have been established according to applicable federal, state, local and institutional guidelines and procedures, and provided that appropriate records of disposal are kept. Drug destroyed on site will be documented in the study files.

## 6 Study Procedures

### 6.1 Overall Study Design

This is an open-label, single-arm, phase II trial of nivolumab, ipilimumab and hypofractionated radiotherapy in adults with newly diagnosed, *MGMT* unmethylated GBM.

Screening begins after the subject's initial eligibility is established and the informed consent form is signed.

If the *MGMT* test was not performed at the study site (NYUSoM), then tumor tissue (archival slides or recent tumor biopsy) must be submitted to the NYUSoM for central confirmation of *MGMT* promoter DNA methylation status. Only subjects centrally confirmed to have unmethylated *MGMT* promoter will be eligible. All subjects must initiate study treatment within 6 weeks of the first diagnostic surgery.

CONFIDENTIAL

This material is the property of the NYU School of Medicine. Do not disclose or use except as authorized in writing by the study sponsor

An initial **Safety Lead-In** of 6 subjects will be conducted to define the safety of nivolumab and ipilimumab in combination with hypofractionated RT as detailed below. Note, the patients enrolled in the Safety Lead-In cohort will subsequently be analyzed in the Main Study Cohort (see below). Also note, special safety provisions are included for the first 3 subjects enrolled (see Section 6.1.1 below). After the initial 6 subjects are enrolled in the Safety Lead-In, enrollment will stop and subjects will be observed for 40 days for **dose-limiting toxicities (DLTs)** and the safety data will be reviewed by the Sponsor and the NYU DSMC. After review of the safety data in the Safety Lead-In, the Sponsor may continue accrual onto the **phase II** portion of the study if the regimen is considered safe, redesign the dosing and schedule of the study treatment with consultation from BMS and the FDA, or stop the study for unacceptable toxicity.

After screening procedures and registration, within 6 weeks of the first diagnostic surgery for glioblastoma, all subjects will initiate study treatment with one dose of nivolumab 3 mg/kg and one dose of ipilimumab 1mg/kg.

- Patients in the **Safety Lead-In/Main Study Cohort** will begin hypofractionated radiotherapy (HFRT) within 1 week of first nivolumab and ipilimumab dose.
- The Surgical Study Cohort will open once the Safety Lead-In is completed. Patients in the **Surgical Study Cohort** will undergo craniotomy and tumor re-resection within 2 weeks from the first dose of nivolumab and ipilimumab. Patients will begin HFRT 3 weeks after surgery.

All subjects will receive HFRT to a total dose of 45 Gy, given in 15 consecutive fractions of 3 Gy each fraction.

All subjects will continue to receive nivolumab 3 mg/kg IV every 2 weeks and ipilimumab 1 mg/kg every 6 weeks from day of first nivolumab and ipilimumab administration.

One treatment cycle will be defined as 42 days (6 weeks), corresponding to 3 doses of nivolumab and one dose of ipilimumab.

Nivolumab and ipilimumab administration will continue for all subjects for 2 years or until disease progression, intolerable toxicity, death, or the subject meets another withdrawal criteria as per the Subject Withdrawal guidelines (Section 6.12), whichever comes first. Subjects who are discontinued from study therapy will enter the post-study follow-up phase of the study as per Section 6.10.

All subjects will be evaluated every 8 weeks with radiographic imaging to assess response to treatment. Disease assessments will be made using standard RANO criteria. However, non-traditional iRANO criteria (Appendix 3) may be considered for patient management. Adverse events will be monitored throughout the trial and graded in severity according to the guidelines outlined in the NCI-CTCAE version 4.03.

The investigator shall take responsibility for and shall take all steps to maintain appropriate records and ensure appropriate supply, storage, handling, distribution and usage of trial treatments in accordance with the protocol and any applicable laws and regulations.

### 6.1.1 **Safety Lead-In**

The first 6 subjects enrolled onto the study will be evaluated as a Safety Lead-In cohort. After all screening, registration and baseline procedures are completed as detailed on the Schedule of Events (Appendix 1), subjects will begin the study regimen.

On Day 1 of Cycle 1, subjects will be administered one dose of nivolumab 3 mg/kg IV and one dose of ipilimumab 1 mg/kg IV.

On Day 8 of Cycle 1, subjects will be administered RT to a total dose of 45 Gy, given in 15 fractions of 3 Gy.

CONFIDENTIAL

This material is the property of the NYU School of Medicine. Do not disclose or use except as authorized in writing by the study sponsor

On Day 15 of Cycle 1, nivolumab 3 mg/kg IV will be administered, and subsequently continue once every 2 weeks.

Ipilimumab 1 mg/kg IV will continue once every 6 weeks after the first ipilimumab dose on Cycle 1 Day 1.

The **DLT evaluation period** will be defined as the **first 53 days** on study. The DLT period will start with the first infusion (**Day 1**) and will **end 4 weeks following the final day of radiation**, ie, **Days 1-53**.

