**The first 3 subjects:**

- The first 3 patients in the safety lead-in will be enrolled in a **staggered fashion**, with at least 2 weeks from time of completion of RT to first dose of study drugs for the subsequent patient.
- For the first 3 subjects, the **maximal tumor diameter may not exceed 5 cm**.
- After the 3rd subject is enrolled, **enrollment will halt and subjects will be observed for 40 days for DLTs (see DLT definitions below)** and to assess overall safety. At the end of the DLT period for the first 3 subjects, the safety data will be reviewed by the Sponsor and the NYU DSMC. If 1 or less of the first 3 subjects experiences a DLT during the DLT observation period, the maximal tumor diameter for subsequent subjects may be increased to **6.6 cm**. If  $\geq 2$  of the first 3 subjects experiences a DLT during the DLT observation period, the study will halt and the sponsor, NYU DSMC, and the FDA, may redesign the dosing and schedule of the study treatment or will stop the study for unacceptable toxicity.
- Continuation of enrollment will occur once all of the first 3 subjects have completed the Day 40 safety assessments and the final safety review decisions have been made.

After the first 6 subjects are enrolled, enrollment will stop and subjects will be observed for 40 days for **DLTs**. After all subjects in the Safety Lead-In cohort have completed the DLT observation period, the safety data will be reviewed by the Sponsor and the NYU DSMC. Continuation of enrollment will occur once all of the subjects have completed the Day 40 safety assessments and the final safety review decisions, including whether the study should be discontinued or proceed to phase II, have been made.

If  $\geq 2$  of the first 6 subjects experiences a DLT during the 40 day DLT observation period, the sponsor, and the FDA, may redesign the dosing and schedule of the study treatment or will stop the study for unacceptable toxicity.

If  $\geq 2$  of the first 6 subjects are unable to complete RT due to toxicity related to the planned treatment, the study will be stopped and the overall safety will be re-assessed by the sponsor and DSMC.

If 1 or less of the first 6 subjects experiences a DLT at the end of the 40 day DLT observation period, the study will continue enrollment onto the phase II part of the study.

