DLT will be determined by toxicities related to nivolumab, ipilimumab, or RT during or beginning over the first 40 days of treatment as defined below. Subjects who experience DLT will be discontinued from study therapy and will enter the post-study follow-up phase of the study. Adverse events that meet DLT criteria but occur outside the DLT window will be classified as unacceptable AEs and study treatment will be discontinued.

Subjects are evaluable for DLTs if they have received at least one dose of nivolumab and ipilimumab, have completed RT per protocol, and have completed safety assessments over the entire DLT evaluation period (days 1 through 40). Any subject who discontinues treatment or withdraws from the study prior to completing the DLT evaluation period for any reason other than the occurrence of a protocol-defined DLT or other AE leading to study treatment discontinuation will be replaced. Each replacement patient will be assigned a unique patient number. Any patient who discontinues after the DLT observation period will not be replaced.

CONFIDENTIAL

This material is the property of the NYU School of Medicine. Do not disclose or use except as authorized in writing by the study sponsor

Subjects who do not experience a DLT during the DLT period (40 days) and remain on study after the DLT period will continue nivolumab and ipilimumab administration for up to 2 years or until the subject discontinues study therapy as per protocol. All subjects who discontinue study therapy will enter the post-study follow-up phase of the study.

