#### 6.1.1.1 **Definition of Dose-Limiting Toxicity (DLT) for the Safety Lead-In**

The DLT period for the Safety Lead-In is considered the first 40 days of study therapy, and will include labs and other evaluations taken at C1D40 (end of the first 40 days). The frequency, time to onset, and severity of toxicities, as well as the success of standard medical management and dosing interruptions/ delays, will be analyzed to determine if a given toxicity should be considered a DLT for dose decision purposes. The final decision of whether or not the AE meets the DLT definition will be based on a careful review of all relevant data by the Sponsor and the NYU DSMC. The treating investigator may also be consulted.

A DLT is defined as any non-hematologic grade  $\geq 3$  adverse event (AE) that is at least possibly, probably or definitely related to nivolumab or ipilimumab or RT during the DLT period with the exceptions noted below.

The following will be classified as DLT:

- Any Grade 2 drug-related uveitis or eye pain or blurred vision that does not respond to topical therapy and does not improve to Grade 1 severity within 7 days OR requires systemic treatment.
- Any Grade  $\geq 2$  drug-related pneumonitis or interstitial lung disease that does not resolve to Grade 1 within 7 days and systemic steroids (also see Pulmonary Adverse Event Management Algorithm in Appendix 4).
- Any Grade 3 drug-related bronchospasm, hypersensitivity reaction, or infusion reaction, regardless of duration.
- Any Grade 3 non-hematologic, drug-related adverse event, with the following criteria:
  - Grade 3 drug-related uveitis, pneumonitis, diarrhea, or colitis of any duration will be classified as DLT.
  - Grade  $\leq 3$  symptoms attributable to brain/intracranial edema that downgrades to Grade  $\leq 2$  within 7 days, or to Grade  $\leq 1$  or baseline within 14 days after onset will not be classified as DLT (for **rules for managing brain/intracranial edema**, see Section 6.2.5 below).
  - Any  $\geq$  grade 2 neurological AE lasting  $> 7$  days will be considered a DLT.
- Grade  $\geq 3$  thrombocytopenia ( $< 50,000 \text{ mm}^3$ ), which will be classified as DLT
- Grade  $\geq 3$  neutropenia ( $\text{ANC} < 1000 \text{ mm}^3$ ), which will be classified as DLT
- Any drug-related liver function test (LFT) abnormality that meets the following criteria will be classified as DLT (also see Hepatic Adverse Event Management Algorithm):

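### The Safety Lead-In go/no-go rules count DLTs over different windows: in Section 3.1.2 one pattern meets both the stop/redesign and the continue rule, and Section 6.1.1 adds a 53-day definition that no rule uses

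*Combined protocol and SAP*

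**What the plan says.** The combined protocol and SAP gives the lead-in window in several places.

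- **Section 6.1.1, definition.** The DLT evaluation period starts with the first infusion and is to "end 4 weeks following the final day of radiation", stated as Days 1-53.
- **Section 6.1.1, rules.** Enrolment pauses for 40 days of observation after subject 3 and again after subject 6. Two or more DLTs among six in 40 days means redesign or stop. The continue rule reads "If 1 or less of the first 6 subjects experiences a DLT at the end of the 40 day DLT observation period". To be evaluable, subjects must "have completed safety assessments over the entire DLT evaluation period (days 1 through 40"). The window also settles what counts: "Adverse events that meet DLT criteria but occur outside the DLT window will be classified as unacceptable AEs".
- **Section 6.1.1.1.** "The DLT period for the Safety Lead-In is considered the first 40 days of study therapy".
- **Sections 7.3.1 and 8.5.** The replacement rule and the summary of stopping rules both use 40 days. Section 8.5 sends the reader to Section 6.1.1 for the detail.
- **Section 3.1.2.** Observation is 40 days and the stop/redesign rule (two or more of six) uses 40 days, but the continue rule (one or fewer of six) is set at 28 days.
- **Synopsis, Study Design.** Observation is 40 days, but both the stop/redesign and the continue rule are set at 28 days.
- **Section 8.6.1.** Phase II accrual is held until the toxicity review has assured that there were no DLTs at all.

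**The concern.** A go/no-go rule works only if its two branches exclude each other, and they do so only when both count events over the same window. Section 3.1.2 breaks this inside one paragraph. The synopsis is consistent within itself but disagrees with Section 6.1.1.

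The window length also bears on the purpose of the lead-in. Section 1.3.3 justifies it by possible overlapping neurotoxicity of immunotherapy and radiotherapy, so the amount of post-radiotherapy time counted matters. A shorter window can only keep or lower the count, so a shorter figure can only make continuing easier. At stake is the first go/no-go decision of the trial.

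**Working it through.** **1. Reproduce the 53-day figure.** Inputs: RT starts on Day 8 with 15 fractions (Section 6.1.1), preferably five days per week (Section 6.4.2).

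- Monday start: fractions on Days 8-12, 15-19 and 22-26, so the last is Day 26. Counting Day 26 as the first of 28 days gives 26 + 27 = Day 53, which matches the protocol. Counting from the next day gives 26 + 28 = Day 54.
- Tuesday to Friday start: the last fraction is Day 28, so the window ends on 28 + 27 = Day 55 or 28 + 28 = Day 56.

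So 53 is a real figure tied to the four-week anchor, not a stray digit.

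**2. Follow-up after the last fraction, weekday schedule.**

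| Window | Last fraction Day 26 | Last fraction Day 28 |
|---|---|---|
| 28 days | 28 - 26 = 2 days | 28 - 28 = 0 days |
| 40 days | 40 - 26 = 14 days | 40 - 28 = 12 days |
| 53 days | 53 - 26 = 27 days | 53 - 28 = 25 days |

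A 40-day window cannot satisfy a definition of four weeks after RT. Even 15 calendar-consecutive fractions, ending on Day 22, leave only 40 - 22 = 18 days.

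**3. Apply the rules to fixed patterns.** Let A be the number of subjects with a DLT by Day 28 and B the number whose first DLT falls on Days 29-40. Section 3.1.2 continues if A ≤ 1 and stops or redesigns if A + B ≥ 2. Both hold whenever A is 0 or 1 and A + B is at least 2.

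| DLT onset (different subjects) | Count at 28 / 40 / 53 days | Synopsis | Section 3.1.2 | Section 6.1.1 rules |
|---|---|---|---|---|
| Days 20 and 35 | 1 / 2 / 2 | continue | both rules met | stop or redesign |
| Days 20 and 45 | 1 / 1 / 2 | continue | continue | continue |
| Day 20 only | 1 / 1 / 1 | continue | continue | continue |

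The first row is the decision conflict. In the second row only the 53-day definition would give two DLTs, and no count rule uses it. The third row passes every count rule but not Section 8.6.1.

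**4. Can 28 days trigger an earlier decision?** No. Section 6.1.1 states: "Continuation of enrollment will occur once all of the subjects have completed the Day 40 safety assessments and the final safety review decisions". The 28-day text can change only which DLTs are counted.

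**5. Would later events be known at the review?** For the first three subjects, yes. Subject 4 cannot start before subject 3 completes Day 40, and subject 6 starts no earlier than subject 4. When subject 6 reaches Day 40, subject 3 is therefore at Day 40 + 39 = 79 or later, and subjects 1 and 2 are further on because they were staggered "with at least 2 weeks from time of completion of RT to first dose of study drugs for the subsequent patient". Their Day 41-53 events will be on hand, so the text should say plainly that these do or do not count.

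**The case against.** The strongest reply is that 40 days plainly governs. Section 6.1.1 limits attribution to toxicities that occur or begin in the first 40 days, and both of its six-subject rules use 40. Section 3.1.2 points to Section 6.1.1.1 for DLT definitions, and that section fixes 40 days. On this view the 53-day sentence is isolated and changes no decision. Much of this stands. A reader might infer that DLTs on Days 20 and 45 should stop the trial, but no stated rule says so. What remains is an explicit definition that contradicts the rules in its own section. It also leaves loose the timing of the three-subject review, which is set by the same term: "At the end of the DLT period for the first 3 subjects, the safety data will be reviewed".

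The reply also notes that the synopsis rules, both at 28 days, cannot overlap with each other. That is correct: the double trigger lies within Section 3.1.2, and the synopsis conflicts only with the 40-day rules elsewhere.

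Finally, the count does not bind mechanically. Section 6.1 lets the sponsor continue if the regimen is considered safe, redesign or stop, and Section 6.1.1.1 leaves DLT adjudication to the sponsor and DSMC. Sections 6.1.1 and 6.2.3 end treatment for a subject with a DLT-type event inside or outside the window. The RT-completion rule, the Bayesian toxicity looks, the 12-subject CNS review and the quarterly DSMC review also apply. All of this limits the harm, but none of it says which count governs the lead-in decision.

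**Conclusion.** The point holds as an inconsistency in the decision rules that should be corrected. Section 3.1.2 can direct opposite actions on the same data, the synopsis disagrees with Section 6.1.1, and Section 6.1.1 carries a definition that its own rules do not follow. The Section 8.6.1 requirement of no DLTs is a separate conflict about the threshold rather than the window. These conclusions rest on the text alone; the 12-14 day figure assumes weekday fractions without interruption.

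Three stronger readings are not supported.

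- A reader might infer that the second ipilimumab dose, due on Day 43, always falls inside 53 days but can be missed by 40. Section 6.2.3 allows longer delays, so it need not fall inside either window.
- A reader might want the chance of wrongly continuing. The documents give neither a DLT risk nor an onset distribution, so no such probability can be relied on.
- A reader might infer that 40 days is left over from a five-fraction course (Days 8-12, and 12 + 28 = 40). The arithmetic fits, but the documents do not say it.

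Nor do the documents show that 40 days is too short a window. They show only that it does not match the stated anchor of four weeks after RT.

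**What to change.** **Minimum change, wording only:**

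- Change 28 to 40 days in the synopsis (both rules) and in the continue rule of Section 3.1.2.
- Remove the 53-day, four-weeks-after-RT definition from Section 6.1.1.
- Align Section 8.6.1 with the rule allowing at most one DLT in six.

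This adds no enrolment time. The C2D1 visit (Day 43 ± 3, so Days 40-46) can carry the end-of-window assessment.

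**If four weeks after RT was intended,** use that window instead in every place: the synopsis, Sections 3.1.2, 6.1, 6.1.1, 6.1.1.1, 7.3.1 and 8.5. Make the same change to Section 8.6.1. The cost is time at each of the two enrolment pauses:

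- Weekday schedule: 53 - 40 = 13 to 56 - 40 = 16 extra days per pause, 26-32 in total.
- RT spread over four weeks, as Section 5.2.2.2 allows: last fraction Day 35, window end 35 + 28 = Day 63, so 23 extra days per pause and 46 in total.
- RT held for 14 days: last fraction Day 40 or 42, window end Day 68 or 70, so 28-30 extra days per pause.

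The C2D15 visit (Day 57 ± 3, so Days 54-60) can serve a window ending on Days 54-56.
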